### 2.2. Study Objectives

- 1 *To obtain additional, long-term, open-label safety and efficacy data for tafamidis in subjects with TTR-CM.*
- 2 *To continue to provide the investigational product tafamidis to subjects with TTR-CM who have completed Protocol Fx1B-201.*

## 3. INTERIM ANALYSES, FINAL ANALYSES AND UNBLINDING

### 3.1. Data Safety Monitoring Board (DSMB)

The study will be reviewed by an independent DSMB to assess the safety of subjects participating in the protocol on an ongoing basis. The DSMB consists of an independent medical monitor (who also serves as chairperson), two external cardiology experts, and an independent statistician. The DSMB will review cumulative safety data on a periodic timetable. Handling of this data is described in detail in the DSMB Charter. The DSMB can recommend that the study team modify or discontinue the trial due to safety concerns.

### **3.2. Additional Interim Analyses**

Given the lack of long-term data in TTR-CM, interim analyses will be performed during the course of the study to allow for the reporting of safety and efficacy data to the scientific community through presentation at scientific and professional meetings or for regulatory purposes. Analyses can also be performed for publication of safety and efficacy data provided there is Pfizer cross functional line review and agreement.

This is an open-label study as such the data will not need to be unblinded.

## **4. HYPOTHESES AND DECISION RULES**

### **4.1. Statistical Hypotheses**

This study is descriptive in nature, and as such, there are no formal hypotheses to be tested.

### **4.2. Statistical Decision Rules**

The data will be summarized using descriptive measures with 95% confidence intervals.

## **5. ANALYSIS SETS**

### **5.1. Safety Analysis Population**

The safety analysis population consists of all subjects who are enrolled in this study and who have taken at least one dose of study medication.

### **5.2. Intention to Treat (ITT) Population**

The intent to treat (ITT) population consists of all subjects who are enrolled in this study, who have taken at least one dose of study medication, and who have baseline and at least one post-baseline cardiac measure. This population will be used for efficacy analysis.

## **6. ENDPOINTS AND COVARIATES**

### **6.1. Efficacy Endpoints**

1. Patient Global Assessment: Severity at each visit and change from baseline
2. Patient Global Assessment: Improvement at each visit
3. New York Heart Association (NYHA) Classification: by category and improvement: at each visit
4. 6-Minute walk test: at each visit and change from baseline
  - a. Distance walked (in meters)
  - b. Categories of distance walked (<300 meters, 300-374.9 meters, 375-449.9 meters, and  $\geq$ 450 meters)
  - c. Pre- and post-baseline dyspnea and fatigue values (using the Borg Scale). This will yield four values for analysis per post-baseline visit. The pre walk test

values, the post walk test values, the within difference value and the change from baseline difference value [that is the difference between the baseline difference value and the visit difference value].

- d. Based on the categories defined in b, subjects will be classified as improved, no change or worsened.
- 5. Kansas City Cardiomyopathy Questionnaire (KCCQ): at each visit and change from baseline
  - a. Physical limitations
  - b. Self-efficacy
  - c. Symptom stability
  - d. Quality of life
  - e. Symptom frequency
  - f. Social limitation
  - g. Symptom burden
  - h. Overall summary score
  - i. Total symptom score
  - j. Clinical summary score

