9.2. Efficacy Analysis

9.2.1. Analysis of Primary Endpoint

For subjects who enroll into this protocol, the cumulative efficacy data (starting from Protocol Fx1B-201) as measured by the Patient Global Assessment, NYHA classification, KCCQ, 6-minute walk test, echocardiograms, and serum levels of troponin I, troponin T, and NT-proBNP will be presented.

Baseline data from protocol Fx1B-201 will be used as baseline for these analyses.

Subjects who enroll into the study and receive any amount of investigational product will be included in the safety population. Subjects who receive any amount of investigational product and have at least one post-baseline efficacy assessment will be included in the efficacy population.

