9.2.2. Patient Global Assessment

Each subject's overall quality of life, as measured by the Patient Global Assessment ([Appendix 1](#)), will be summarized using descriptive statistics. In addition, the percentage of subjects with unchanged, worsened, or improved global assessments (and 95% confidence intervals) will be presented at each scheduled assessment.

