Appendix 1. Patient Global Assessment

Patient Global Assessment:

At Baseline, the Patient Global Assessment will be:

“In general, how do you feel today?”

- Excellent
- Very good
- Good
- Fair
- Poor

At each follow-up visit, the Patient Global Assessment will be:

“How do you feel today as compared to when we last talked with you for a study visit?”

- Markedly improved
- Moderately improved
- Mildly improved
- Unchanged
- Mildly worsened
- Moderately worsened
- Markedly worsened

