#### 8.1.2. Analyses for Categorical Data

All categorical data will be summarized as n, percentage and 95% confidence intervals. The 95% CI intervals will be estimated using exact methods due to the decreasing sample size. In addition, a shift table will be provided for such variables as the 6 minute walk test, PGA, and NYHA class.

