## 8.2. Efficacy Analyses

Efficacy analyses will be performed for cumulative efficacy data as measured by Patient Global Assessment (PGA), New York Heart Association (NYHA) classification, Kansas City Cardiomyopathy Questionnaire (KCCQ), 6-minute walk test (6MWT), echocardiograms, and serum levels of troponin I, troponin T, and NT-proBNP.

The analyses will use the methods described above for these continuous outcomes in [Section 8.1.1](#):

- Kansas City Cardiomyopathy Questionnaire (KCCQ)
- 6-minute walk test (6MWT)
- Echocardiograms
- Serum levels of troponin I, troponin T, and NT-proBNP.

The analyses will use the methods described above for these categorical outcomes in [Section 8.1.2](#):

- Patient Global Assessment (PGA)
- New York Heart Association (NYHA) classification
- 6-minute walk test (6MWT) (categorized by level as described below)

Shift tables will be provided for the following variables:

- Patient Global Assessment (PGA)
- New York Heart Association (NYHA) classification
- 6-minute walk test (6MWT) (categorized as stable, improved, worsened)

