## **APPENDICES**

### **Appendix 1. Data Derivation details**

#### **Appendix 1.1. KCCQ (See protocol for a copy of the questionnaire)**

## **The Kansas City Cardiomyopathy Questionnaire Scoring Instructions**

There are 10 summary scores within the KCCQ, which are calculated as follows:

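### On the documented form, PGA severity at follow-up, its change from baseline and the PGA shift table have no follow-up input

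*SAP*

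**What the plan says.** SAP 6.1 gives PGA two separate endpoints. Item 1 is "Patient Global Assessment: Severity at each visit and change from baseline"; item 2 is improvement at each visit. SAP 8.1.2 adds that "a shift table will be provided for such variables as the 6 minute walk test, PGA, and NYHA class". SAP 8.2 repeats the commitment ("Shift tables will be provided for the following variables") and puts PGA first in the list.

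Protocol 7.1 names Protocol Appendix 1 as the PGA form. That appendix holds two different questions. The first is introduced by "At Baseline, the Patient Global Assessment will be" and asks how the subject feels in general today, on five levels from excellent to poor. The second, for each follow-up visit, is "How do you feel today as compared to when we last talked with you for a study visit", on seven levels from markedly improved to markedly worsened.

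Protocol 9.2.2 asks for descriptive statistics and for "the percentage of subjects with unchanged, worsened, or improved global assessments" at each scheduled assessment. Protocol 9.2.1 lists PGA among the cumulative efficacy data and then says, for all of them, "Baseline data from protocol Fx1B-201 will be used as baseline for these analyses".

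**The concern.** Severity at a visit, change in severity from baseline, and a shift table all need the same state scale at baseline and at follow-up. The documented form supplies that scale once, at baseline. A programmer following the plan as written would have either nothing to put in these outputs or a cross-tabulation of two different questions presented as a shift in one variable.

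A second risk concerns the result that can be produced. The percentages in Protocol 9.2.2 come from a question whose reference is the last study visit. Read under the general sentence in Protocol 9.2.1, they could be reported as change from the pre-treatment baseline of Fx1B-201, which is a different quantity. SAP 3.2 foresees interim reporting of efficacy data at scientific meetings, for regulatory purposes and in publications, so such a table could circulate outside the study report.

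**Working it through.** The plan states no figure that depends on this point, so there is none to reproduce. The check sets the planned results beside the documented form and then asks whether any rule could bridge the gap.

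**1. Planned results against the form**

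| Planned PGA result | Needs at follow-up | Documented at follow-up (Protocol Appendix 1) | Supported? |
|---|---|---|---|
| Severity at each visit (SAP 6.1 item 1) | 5-level state | 7-level change since last study visit | No |
| Change from baseline (SAP 6.1 item 1) | 5-level state | as above | No |
| Shift table (SAP 8.1.2, 8.2) | Same scale as baseline | as above | No |
| Improved, unchanged, worsened (Protocol 9.2.2, SAP 6.1 item 2) | A direction of change | as above | Yes, against the last study visit |

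The two scales have no level in common.

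**2. Is there a linking rule?** SAP 7 sends the reader to SAP "Appendix 1. Data Derivation details" for scoring. That appendix covers KCCQ, the 6-minute walk categories and QTc, but not PGA, and no PGA rule appears elsewhere in the SAP. Absence from the appendix is not a fault in itself. NYHA is absent too and needs no rule, because the same four classes apply at every visit. The 6-minute walk has an explicit rule comparing baseline category with visit category. PGA is the only variable in the SAP 8.2 shift-table list with neither a common scale nor a rule.

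**3. Could change from baseline be rebuilt by chaining the visit-to-visit answers?** Not without a further rule.

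- Direction: two successive answers give 7 × 7 = 49 patterns. One improved and one worsened answer occur together in 2 × 3 × 3 = 18 of them. In those 18 the net direction is undetermined. This counts patterns; it does not estimate how often they would occur.
- Level: start at good, and assume only that improved means the same level or higher and worsened the same level or lower. After mildly improved, the subject may be at good, very good or excellent. After a following mildly worsened, all 5 levels are possible.

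**4. What is the reference of the follow-up question?** Protocol 6.2.1 schedules telephone contacts at month 3 and then every 6 months, and itself calls them phone visits. No PGA is scheduled at them. A subject answering at a clinic visit could be comparing with the phone contact or with the previous clinic visit. This is a further obstacle to chaining, and a reason to title the results in the form's own terms.

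**The case against.** The strongest reply is that the CRF may hold both answers. SAP 6.1 lists severity and improvement as separate items, which is how a team with both a state and a change question would write it. The fault would then lie in an incomplete protocol appendix. This stands as a possibility. A reader might infer from the mismatch that follow-up severity was never collected; the documents do not support that, because the CRF is not among them. They show only that the form the protocol names does not contain it. Even if both questions were asked, the SAP still needs to cite the form that supplies the data and define the table.

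A second reply is that Protocol 9.2.2 never says its percentages are from baseline, whereas Protocol 9.2.3 does say so for NYHA. The SAP's own Fx1B-201 baseline rule sits in 8.1.1, for continuous data, while PGA is analysed under 8.1.2. This also stands. A reader might infer that the improved, unchanged and worsened percentages are invalid. They are not: the PGA-specific text fits the change question. What remains is the risk that the general sentence in Protocol 9.2.1 is applied to them.

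A reader might also infer that a subject who worsens once and then reports no change at later visits is known to be worse than at the start of Fx1B-303. That does not follow, because the ambiguous reference visit leaves status against the start undetermined.

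Finally, a table of baseline state by follow-up change category can be printed. It can, but it crosses two questions, and the SAP does not define or label such a table.

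**Conclusion.** The point holds for the form as documented. PGA severity at each visit, PGA change from baseline and the PGA shift table have no valid follow-up input, and the SAP gives no rule that would create one. The percentages improved, unchanged and worsened are valid as change since the last study visit and should not be presented as change from the Fx1B-201 baseline.

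The size is modest. SAP 4.1 states that there are no formal hypotheses, and the protocol expects up to 35 subjects and ranks none of the efficacy endpoints. No test or decision is affected, and individual answers will remain visible in the subject listings. What is affected is one listed endpoint, one promised table, and the labelling of a third result.

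The conclusion rests on one assumption that cannot be tested here: that the CRF matches Protocol Appendix 1. If the CRF also asked the 5-level question at follow-up, the data exist and the defect is one of documentation.

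**What to change.** Check the CRF first, then take one branch.

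- **State question also asked at follow-up:** cite that form in the SAP, and define PGA severity, change from baseline and the shift table on the 5-level scale, as baseline level by visit level.
- **State question not asked at follow-up:** delete PGA severity at each visit, PGA change from baseline and the PGA shift table for Fx1B-303 visits from SAP 6.1, 8.1.2 and 8.2.

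Wherever improved, unchanged or worsened results come from the 7-level question, title them as since last study visit, as worded on the form, and footnote that they are not change from the Fx1B-201 baseline. Do not put this title on categories derived from a follow-up state question, for which it would be wrong.

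The cost is one CRF check, a few lines of SAP text, table titles and a footnote. No new data are needed. It is best done before the PGA tables are programmed or next reported.

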1.2.2. Study Rationale

The initial development activities for tafamidis were undertaken in patients with TTR-FAP. Safety data in this population, and the results from the TRACS study, led to the initiation of Protocol Fx1B-201, a 12-month trial of tafamidis in patients with TTR-CM. The results of the Fx1B-201 study will be used in the design of a Phase 3 program that will evaluate the efficacy and safety of tafamidis in TTR-CM.

TTR-CM is a slowly progressing disease with a median survival of approximately 60 months [14, 15]. It is currently not known whether tafamidis will be effective in slowing or halting the progression of TTR amyloid cardiomyopathy, or when such an impact would become evident. Therefore, the purpose of the current study is to assess the long-term safety and

efficacy of tafamidis in patients with ATTR-CM. Eligible patients who successfully completed Protocol Fx1B-201, having received open-label tafamidis for 12 months, may enroll in Protocol Fx1B-303 and continue to receive open-label tafamidis for up to an additional 10 years.

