9.2.4. Kansas City Cardiomyopathy Questionnaire

The Kansas City Cardiomyopathy Questionnaire (KCCQ, [Appendix 3](#)) will be summarized by the following summary scores calculated using the guidelines established in the KCCQ Scoring Instruction Manual:

Physical limitations	Self-efficacy
Symptom stability	Quality of life
Symptom frequency	Social limitation
Symptom burden	Overall summary score
Total symptom score	Clinical summary score

Change from baseline for each summary score of the KCCQ will be analyzed using a mixed model analysis (with baseline value as covariate, subjects as random effect, and time as fixed effect). Data will also be summarized by each scheduled assessment and a graphical presentation of these data will be presented.

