Appendix 3. Kansas City Cardiomyopathy Questionnaire

The KC Cardiomyopathy Questionnaire

Study ID#

The following questions refer to your **heart failure** and how it may affect your life. Please read and complete the following questions. There are no right or wrong answers. Please mark the answer that best applies to you.

1. **Heart failure** affects different people in different ways. Some feel shortness of breath while others feel fatigue. Please indicate how much you are limited by **heart failure** (shortness of breath or fatigue) in your ability to do the following activities over the past 2 weeks.

Activity	Please place an X in one box on each line					
	Extremely Limited	Quite a bit Limited	Moderately Limited	Slightly Limited	Not at all Limited	Limited for other reasons or did not do the activity
Dressing yourself						
Showering/Bathing						
Walking 1 block on level ground						
Doing yardwork, housework or carrying groceries						
Climbing a flight of stairs without stopping						
Hurrying or jogging (as if to catch a bus)						

2. Compared with 2 weeks ago, have your symptoms of **heart failure** (shortness of breath, fatigue, or ankle swelling) changed?

My symptoms of **heart failure** have become...

Much worse	Slightly worse	Not changed	Slightly better	Much better	I've had no symptoms over the last 2 weeks
					

Study ID#

3. Over the past 2 weeks, how many times did you have **swelling** in your feet, ankles or legs when you woke up in the morning?

	3 or more times				

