## 8. STATISTICAL METHODOLOGY AND STATISTICAL ANALYSES

### 8.1. Statistical Methods

#### 8.1.1. Analyses for Continuous Data

All continuous data will be summarized with descriptive statistics, including mean, standard deviation, median, IQR, range and 95% confidence intervals. In addition, change from baseline statistics will be presented as appropriate, to include the appropriate descriptive statistics. For analysis of change from baseline, baseline data from protocol Fx1B-201 will be used as baseline for these analyses. For the change from baseline statistics, the estimate will be adjusted for baseline and the LSMean and standard error will be presented with the 95% confidence interval based on an MMRM model with a random effect for subject and covariate of baseline.

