### **2. Symptom Stability**

- Code the response to Question 2 as follows:

Much worse = 1  
Slightly worse = 2  
Not changed = 3  
Slightly better = 4  
Much better = 5  
I've had no symptoms over the last 2 weeks = 3

- If Question 2 is not missing, then compute

Symptom Stability Score =  $100 * [(Question\ 2) - 1] / 4$

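### KCCQ Symptom Stability is already a two-week change rating, so modelling its change from the Fx1B-201 baseline compares two short-term trends and does not measure cumulative symptom change

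*SAP*

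**What the plan says.** Protocol Appendix 3, question 2, opens "Compared with 2 weeks ago, have your symptoms of" and goes on to ask whether heart failure symptoms have changed. SAP Appendix 1.1 (2. Symptom Stability) codes the answers 1 to 5 and rescales them to 0–100. Two of its coding lines are "Slightly worse = 2" and "I've had no symptoms over the last 2 weeks = 3". The second puts a subject without symptoms on the same code as one whose symptoms have not changed.

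SAP 6.1 item 5 defines the endpoint as "Kansas City Cardiomyopathy Questionnaire (KCCQ): at each visit and change from baseline", with Symptom Stability as item c of ten scores. Protocol 9.2.4 says "Change from baseline for each summary score of the KCCQ will be analyzed using a mixed model analysis", and Symptom Stability is in its list. SAP 8.2 routes the KCCQ to SAP 8.1.1, which gives a baseline-adjusted LSMean, standard error and 95% CI "based on an MMRM model with a random effect for subject and covariate of baseline". The reference point is the parent study: "baseline data from protocol Fx1B-201 will be used as baseline for these analyses". Neither document exempts Symptom Stability or gives it its own interpretation.

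The same sections also plan descriptive statistics of the score at each visit. SAP 8.1.1 includes 95% CIs for these, and protocol 9.2.4 adds a graph.

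**The concern.** For a level-type score, such as symptom frequency, visit minus baseline is the net change since baseline. Symptom Stability is not a level. Each value already describes movement over the preceding 2 weeks, so the difference between two values says whether the recent trend differs from the recent trend before first dose. It does not say how far symptoms have moved in between.

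The plan gives this difference the same label and model as the nine level-type scores beside it. A reader would naturally take an LSMean near zero as preserved symptoms and a positive one as improvement. The study's purpose is long-term efficacy data in a progressive disease, it has no control group (protocol 3.1), and SAP 3.2 foresees interim results going to meetings, regulators and publications. A mislabelled column has no comparator to expose it.

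**Working it through.** The plan states no figure for this score, so there is none to reproduce. The check applies the SAP's own scoring rule.

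**Inputs**
- Score = 100 × (Q2 − 1) / 4 (SAP Appendix 1.1). *Much worse* (1) gives 0, *slightly worse* (2) 25, *not changed* (3) 50, *slightly better* (4) 75, *much better* (5) 100. *No symptoms* is coded 3 and gives 50.
- Baseline: last measurement before first dose in Fx1B-201 (SAP 6.7, 8.1.1).
- Follow-up: subjects had 12 months in Fx1B-201 and may "continue to receive open-label tafamidis for up to an additional 10 years" (protocol 1.2.2), so about 1 + 10 = 11 years at most from the analysis baseline.
- Assessment: every 6 months, months 6 to 114 (protocol 6.2.2), which is 114 / 6 = 19 scheduled clinic visits before the end-of-study visit.

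**Step 1: response patterns.** Change = visit score − baseline score.

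| Baseline rating | Rating at every later visit | Change | Visit score − 50 |
|---|---|---|---|
| not changed | not changed | 50 − 50 = 0 | 0 |
| slightly worse | slightly worse | 25 − 25 = 0 | −25 |
| much worse | much worse | 0 − 0 = 0 | −50 |
| slightly better | slightly better | 75 − 75 = 0 | +25 |
| slightly worse | not changed | 50 − 25 = +25 | 0 |
| not changed | slightly worse | 25 − 50 = −25 | −25 |
| slightly better | no symptoms | 50 − 75 = −25 | 0 |

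The first four rows are four different courses with one change value. In the fifth row symptoms stopped worsening but nothing was regained. In the sixth the −25 is the same at the first visit and the nineteenth. In the last, a subject who becomes symptom-free is recorded as falling by 25.

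**Step 2: does the baseline covariate help?** Write the expected visit score as a + b × baseline, and let M be the mean baseline. The LSMean change at M is a + (b − 1)M = (a + bM) − M, that is, the adjusted visit mean minus the mean baseline. Suppose a share p of subjects rate *slightly worse* at baseline and throughout, and the rest *not changed* throughout. Both the baseline mean and every visit mean are then 25p + 50(1 − p):
- p = 0: 50 − 50 = 0
- p = 0.5: 37.5 − 37.5 = 0
- p = 1: 25 − 25 = 0

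The LSMean change is zero for every p, so adjustment does not separate the groups. The by-visit means (50, 37.5, 25) do.

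**Step 3: coverage of the item.** A 2-week recall covers 14 / 182.6 = 7.7% of a 6-month interval. A subject who declines too slowly to notice over 2 weeks answers *not changed* each time and scores 50, on either scale.

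**Step 4: spread to other scores.** Under SAP Appendix 1.1, the Total Symptom score uses frequency and burden; the Clinical Summary adds physical limitation; the Overall Summary further adds quality of life and social limitation. Symptom Stability enters none of them.

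**The case against.** Four arguments on the other side have force.

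- **Most of the remedy is already planned.** The by-visit score with a 95% CI is an existing output and distinguishes 25 from 50. Step 2 also shows that a reader can recover the adjusted visit mean by adding back the mean baseline, which SAP 6.7 says will be summarised. This stands, and it limits the defect to the change and model output.
- **The difference is not meaningless.** Protocol 1.2.2 asks whether tafamidis slows or halts progression. Moving from *slightly worse* before first dose to *not changed* on treatment is a shift in recent trajectory and bears on that. This stands too. What fails is the label: that shift is not a gain in symptoms since baseline.
- **Reading against 50 does not rescue the item.** The slow decliner in Step 3 looks stable on either scale. This is a limit of a 2-week question asked twice a year, and the plan should state it.
- **Nothing decisive rests on it.** The study tests no hypotheses (SAP 4.1). Symptom frequency and burden, NYHA class, the 6-minute walk and NT-proBNP are all planned and could show decline. This sets the severity; it does not make the modelled number a measure of cumulative change.

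A reader might also infer that steady decline always gives a change of zero. The documents do not support that: zero needs the same rating at baseline and later, and decline beginning after a stable baseline gives −25. The distribution of question 2 at the Fx1B-201 baseline is not reported, so how often the zero pattern would occur is unknown.

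**Conclusion.** The point holds in a narrow form. For Symptom Stability, change from the Fx1B-201 baseline and its mixed-model LSMean compare two 2-week trends, up to about 11 years apart, and do not measure cumulative symptom change. In constructed cases the value can be 0 under continued worsening, +25 with nothing regained, or a flat −25 under continuing decline. These show what the statistic can do; they are not estimates of its size in this trial, which the documents do not allow.

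It would be too strong to conclude that the KCCQ results as a whole are compromised or that the plan cannot see decline. One score of ten is affected, the composites do not use it, and its by-visit summary is sound apart from the merged *no symptoms* code. No error rate or sample size is at stake. Severity is minor.

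The conclusion rests on the scoring and question wording in the documents, and on reading the KCCQ instructions in protocol 9.2.4 and SAP 6.1, 8.1.1 and 8.2 as covering all ten scores, since no exception is written.

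**What to change.** In protocol 9.2.4 and SAP 6.1 item 5, 8.1.1 and 8.2:

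1. Exempt Symptom Stability from the change-from-baseline statistics and the mixed model. Keep both for the other nine scores.
2. Keep the planned by-visit score with its 95% CI, and state that it is read against the neutral value 50.
3. Add by-visit counts and percentages of worse, not changed and better over the prior 2 weeks, with the exact intervals of SAP 8.1.2. Show *no symptoms* as its own category, taken from the raw answer because the coded value merges it with *not changed*.
4. State that a 2-week item asked every 6 months cannot detect slow decline even against 50, and that long-term symptom change rests on the symptom frequency, symptom burden and total symptom scores. Those also use a 2-week recall but rate how often or how much, so their differences are changes in level.

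The cost is a wording change, one by-visit table and the loss of one model output, including its comparison of recent trend with the pre-treatment trend. No new data are needed, assuming the item-level answers are kept in the database. Protocol section 9 lets the SAP modify protocol plans, but protocol 9.2.4 should be aligned at the next amendment so that the two documents agree.
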